#### 13.2 Statistical Analysis Plan

Patient demographic and baseline characteristics, including age, gender, medical history, and prior cGVHD therapy, will be summarized using descriptive statistics. For continuous variables, descriptive

statistics (number [n], mean, standard deviation, standard error, median (range) will be provided. For categorical variables, patient counts and percentages will be provided.

The overall response rate (CR+PR) will be calculated as the percent of evaluable patients; exact 95% confidence intervals will be calculated for these estimates. Response rates will also be evaluated based on number and type of prior therapy(ies). Time to response, duration of response, and survival will be estimated using the product-limit method of Kaplan and Meier.

Observed toxicities will be summarized in terms of type (organ affected or laboratory determination), severity, time of onset, duration, probable association with the study treatment and reversibility or outcome. Baseline information (e.g. the extent/type of prior therapy) and demographic information will be presented as well to describe the patients treated in this study.

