### 1.2 Secondary Objectives

- Characterize and evaluate toxicities, including type, frequency, severity, attribution, time course and duration.
- Estimate overall and failure-free survival, non-relapse mortality (NRM) and relapse, through 1 year after initiation of treatment.
- Characterize chronic GVHD Symptom Scale scores -self-report (with assistance from RNs and MDs).
- Determine ongoing prednisone use with IL-2 and ECP combination therapy.
- To assess efficacy of protocol therapy ( IL-2+ECP) in helping to decrease the steroid dosage.
- Assess the immunologic effects of low-dose daily SC IL-2 + ECP.
- Correlate clinical endpoints of response with ECP performance parameters.

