### **5.5 Criteria for Removal from Treatment**

- Subject withdraws consent
- Non-compliance
- Administrative reasons (insurance loss or no coverage of IL-2 or ECP by third party payors)
- Any Grade 4 non hematologic adverse event
- Life threatening anaphylactic reaction to IL-2
- Recurrent or non-resolving grade 3 toxic event
- Malignant relapse
- Clinical worsening of GVHD requiring the addition of a new immunosuppressive medication. A 50% increase in the corticosteroid dose will be considered evidence of worsening GVHD. Changes in other immunosuppressive medication doses to maintain a therapeutic level alone will not be criteria for removal from the trial.

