**Failure-free Survival:**

Defined as the time interval from date of first dose of study drug to first documented cGVHD progression (necessitating change of treatment), malignancy relapse or progression or death from any cause, whichever occurs first.

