**Non-Relapse Mortality:**

Defined as time interval from date of first dose of study drug to death from any cause among patients without active disease.

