### 13.1 Study Design, Sample Size, and Accrual Rate

This single center/single arm, phase II clinical trial is designed to evaluate the anti-cGVHD activity of extracorporeal photopheresis (ECP) when combined with low dose IL-2, in patients with steroid refractory cGVHD, as assessed by overall cGVHD response rate (CR+PR+SD). The primary endpoint overall response (CR+PR+SD) is based on the NIH cGVHD consensus criteria; calculated as the percent of evaluable patients that have confirmed CR/PR or SD

This study will implement a Simon, optimal, two-stage design to evaluate the anti-cGVHD activity of the ECP/IL-2 regimen. The trial is expected to enroll 24 patients e sample size is based on the desire to discriminate a promising response rate of 50% from a current response rate of 25%. The null hypothesis

that the true response rate is 25% will be tested against a one-sided alternative. In the first stage, 9 patients will be accrued. If there are 2 or fewer responses in these 9 patients, the study will be stopped. Otherwise, 15 additional patients will be accrued for a total of 24. The null hypothesis will be rejected if 10 or more responses are observed in 24 patients. This design yields a type I error rate of 0.05 and power of .80 when the true response rate is 50%. Currently, about 20-25 new patients are referred to ECP per year. We expect that 6 patients to be enrolled per year with the expected completion of accrual in 4 years.

**Evaluable for Response:** As part of the primary analysis, patients will be considered evaluable for response if they are eligible, have baseline disease assessments, and receive protocol treatment of any duration. All such patients will be evaluated for clinical response. Our primary outcome will be the clinical response rate measured in all patients who are enrolled and receive any amount of protocol therapy.

Patients who are consented for the study but withdraw for any reason (progression of GVHD, infectious complications, insurance denial etc) prior to initiation of protocol therapy will not be eligible for response evaluation.

**Evaluable for Toxicity:** Patients will be considered evaluable for toxicity if they receive any study drug.

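### Kaplan-Meier is assigned to time to response with no rule for death, relapse or new therapy before response, and NRM and relapse have no stated estimator

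*Combined protocol and SAP*

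**What the plan says.** - **Estimator.** Section 13.2 gives one sentence on time-to-event methods: "Time to response, duration of response, and survival will be estimated using the product-limit method of Kaplan and Meier". It states no censoring rule and no competing event. Cumulative incidence and competing risks are not mentioned anywhere in the document.
- **Events that can come before response.** Section 5.5 lists reasons for leaving treatment, including malignant relapse and "Clinical worsening of GVHD requiring the addition of a new immunosuppressive medication". Section 11.1.1 also lets patients stop IL-2 and start other immunosuppression without meeting the NIH criteria for progression. Death is a further route.
- **Response denominator.** Section 13.1 counts as evaluable every eligible patient with a baseline assessment who receives any protocol treatment, so early failures stay in the response rate.
- **NRM and relapse.** Section 1.2 sets the aim: "Estimate overall and failure-free survival, non-relapse mortality (NRM) and relapse, through 1 year after initiation of treatment". Section 11.2 gives NRM as follows: "Defined as time interval from date of first dose of study drug to death from any cause among patients without active disease". Section 11.2 does not define relapse as an endpoint, and 13.2 names no estimator for NRM or relapse.
- **Failure-free survival.** Section 11.2 runs this endpoint to "first documented cGVHD progression (necessitating change of treatment), malignancy relapse or progression or death from any cause, whichever occurs first".
- **Follow-up.** Section 5.2.1 says that no protocol-specific follow-up data are collected after the first 12 weeks.

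**The concern.** A patient who dies, relapses or moves to another systemic agent before responding can no longer respond to IL-2 plus ECP alone. If that patient is censored, Kaplan-Meier assumes the same future chance of response as for those still under observation. The curve then rises above the proportion who actually respond. The response rate keeps these patients as non-responders, so one report could contain two response figures that disagree, with the curve always the higher.

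For NRM the trouble lies in the definition. The restriction to deaths "death from any cause among patients without active disease" can refer to cGVHD or to the malignancy. The document uses the word disease for both: progressive disease in 11.1.1 means cGVHD, while disease relapse in 2.1.1 means malignancy. Under either reading, membership of the group is settled only after the first dose, so the endpoint conditions on a later state. With no estimator, and no statement that relapse and NRM compete, two analysts could report different values from the same data.

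**Working it through.** **The plan's own figure.** The plan gives no number for time to response or NRM. Its only reproducible figure here is the Simon design: stop if 2 or fewer of 9 respond, reject if 10 or more of 24 respond. Summing over first-stage counts x = 3 to 9, P(reject) = Σ b(x; 9, p) × P(Bin(15, p) ≥ 10 − x). This gives 0.0485 at p = 0.25 and 0.8055 at p = 0.50, in line with the stated 0.05 and 0.80. The calculation uses response counts only, so the choice of time-to-response estimator does not enter it.

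**Inputs for time to response.** True cumulative response is set at 25% and 50%, the two rates in 13.1. The competing-event rate comes from the background cohort in 2.1.1: 56% six-month failure-free survival, with failures made up of 34% third-line therapy, 7% NRM and 3% relapse (34 + 7 + 3 = 44 = 100 − 56).

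**Scaling to the treatment period.** At constant hazard, failures by week 12 are 1 − 0.56^(12/26) = 23.5%. By week 16, the last response assessment, they are 1 − 0.56^(16/26) = 30.0%.

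**Formula.** Let C_e be the true cumulative incidence of response and C_c that of competing events, with constant cause-specific hazards and competing events censored when they occur. Then 1-KM = 1 − (1 − C_e − C_c)^(C_e/(C_e + C_c)).

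Worked case: C_e = 0.50, C_c = 0.235. 1 − (0.265)^(0.50/0.735) = 0.595.

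| Competing events | True 50% appears as | True 25% appears as |
|---|---|---|
| 5% | 51.6% | 25.7% |
| 10% | 53.4% | 26.5% |
| 20% | 57.7% | 28.3% |
| 23.5% | 59.5% | 29.0% |
| 30% | 63.4% | 30.4% |

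The overstatement runs from 0.7 to 13.4 points.

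**A check without constant hazards.** Take 24 patients assessed at weeks 3, 7, 9 and 12, with 3, 4, 3 and 2 responses and 1, 1, 2 and 1 competing events. The numbers at risk are 24, 20, 15 and 10. Censoring gives 1 − (21/24)(16/20)(12/15)(8/10) = 55.2%, although 12/24 = 50.0% responded. Keeping the failures in the risk set as non-responders gives 1 − (21/24)(17/21)(14/17)(12/14) = 50.0%. The bias therefore comes from the unstated censoring rule.

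**NRM.** With 7% NRM and 3% relapse at six months, censoring at relapse gives 1 − 0.90^0.7 = 7.1% against 7.0%. Dropping relapsed patients from the denominator gives 7/97 = 7.2%. Doubling the hazards to reach 12 months gives a cumulative incidence of 0.7 × (1 − 0.81) = 13.3%, against a 1-KM of 1 − 0.81^0.7 = 13.7%. One patient in 24 is 4.2 points, so these differences are negligible.

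**The case against.** The strongest reply on time to response is that 13.2 never says early failures will be censored. Section 13.1 keeps every treated patient evaluable, and if early failures stay at risk to the end of the window with complete follow-up, 1-KM equals the cumulative incidence. A curve among responders only also avoids the bias. This stands, and it is why the bias is conditional. It does not remove the need for a rule, because the text supports neither version and censoring is what an analyst would ordinarily do.

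Constant hazards may also overstate the effect. If stable disease counts as response, as in 13.1, many patients would qualify at the week 3 visit, before most switches, and responses that come before the competing events carry no bias. This also stands. In addition, time to response is neither a listed objective nor a defined endpoint.

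Three stronger readings are tempting but are not supported:

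- A reader might infer that NRM too would be estimated with bias. The Kaplan-Meier sentence does not list NRM, and the effect on the background rates is about 0.1 point at six months. A larger figure of 8.8% arises only if NRM is also censored at change of therapy, and no section says that.
- A reader might infer that nobody enrolled could have an NRM event, because all have active cGVHD at entry. A patient in complete response who then died would count, and under a heading of non-relapse mortality the malignancy reading is the more natural one.
- A reader might apply the six-month 34% switch rate directly and obtain 66.4% for a true 50% and 31.5% for a true 25%. That sets a six-month rate against a 12-week course. Scaled to 12 weeks, the switch share is 23.5% × 34/44 = 18.1%, which gives 56.8% and 27.9%.

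**Conclusion.** The point holds as a gap in specification that could bias a descriptive summary upward. If competing events are censored, the overstatement is about 9.5 points at a true 50% and 4 points at a true 25% on the scaled background rate, and about 1 to 13 points over a 5% to 30% range. This assumes constant cause-specific hazards and that the background cohort's failure rate carries over to this trial. It falls to zero under either alternative handling described above.

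For NRM and relapse the fault is an ambiguous definition and a missing method, and no material numerical bias is shown. The Simon decision and the sample size of 24 are untouched, as is the response rate with its exact interval. Kaplan-Meier is suitable for overall and failure-free survival, because both count death as an event. The conflict between a one-year horizon in 1.2 and no protocol-specific follow-up after 12 weeks in 5.2.1 threatens the NRM and relapse estimates more than the choice of estimator does.

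**What to change.** - **Section 13.2, response.** Estimate time to response by cumulative incidence (Aalen-Johansen), with death, malignant relapse and start of new systemic therapy as competing events. State the end of the assessment window.
- **Section 11.2.** Define NRM as death without prior relapse or progression of the malignancy, and define relapse as an endpoint.
- **Section 13.2, NRM and relapse.** Estimate them as mutually competing cumulative incidences. Keep Kaplan-Meier for overall and failure-free survival.
- **Sections 1.2 and 5.2.1.** Reconcile the one-year horizon with the 12-week limit on data collection. Section 12.1.3 lists follow-up and survival forms but points to no visit schedule that would settle this.

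The estimator and definition changes are wording only. If the one-year horizon is kept, vital status, relapse status and their dates must be collected to one year for each patient. That is a small addition in a trial of 24, but it is a real one if the 12-week limit is currently applied.

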## **14.0 Human Subject Issues**

### **14.1 Institutional Review Board**

In accordance with City of Hope policies, an Institutional Review Board (IRB) that complies with the federal regulations at 45 CFR 46 and 21 CFR 50, 56 and State of California Health and Safety code, Title 17, must review and approve this protocol and the informed consent form prior to initiation of the study. All institutional, NCI, Federal, and State of California regulations must be fulfilled.

### **14.2 Recruitment of Subjects:**

Subjects will be recruited from City of Hope

### **14.3 Advertisements**

Although none are planned, advertisements to include print, media (radio, television, billboards), telephone scripts, lay summary to be posted on City of Hope's public Clinical Trials On-LineSM website, etc., will be reviewed and approved by the IRB prior to their use to recruit potential study subjects.

### **14.4 Study location and Performance Sites**

This study will be performed at COH.

### **14.5 Confidentiality**

This research will be conducted in compliance with federal and state of California requirements relating to protected health information (PHI).

The study will record individual immunological, clinical response and side effect profile to IL-2 and ECP combination therapy and the information collected will be linked to the subject's identity using a coded study number. In addition, results of screening tests to rule out HIV, HBC, and HCV performed in the Department of Transfusion Medicine will be used with the participant's permission if performed in the past 4 months. The principal investigator, co-investigators, and laboratory technicians will have access to this information, but all information will be treated confidentially. No identifiers will be used in any subsequent publication of these results.

### **14.6 Financial Obligations and Compensation**

Cost for IL-2 and ECP will be covered by third party payers the enrolled subjects will not bear the cost of treatment. The cost for immunologic studies will be covered by in house funding support. Intramural funding will also be used to cover cost of personnel and biostatistical analysis of data generated from this clinical trial. Our past experience suggests that insurance coverage rate is 60%. Patients who sign consent but are not eligible for IL-2 in case insurance is unwilling to pay for IL-2 will be deemed as screen failures

and will not be eligible for final evaluation. They will continue regular follow up and standard of care treatment.

The standard of care drug(s) and procedures provided will be the responsibility of the research participant and/or the insurance carrier. The research participant will be responsible for all copayments, deductibles, and other costs of treatment and diagnostic procedures as set forth by the insurance carrier. The research participant and/or the insurance carrier will be billed for the costs of treatment and diagnostic procedures in the same way as if the research participant were not in a research study. However, neither the research participant nor the insurance carrier will be responsible for the research procedures related to this study.

In the event of physical injury to a research participant, resulting from research procedures, appropriate medical treatment will be available at the City of Hope to the injured research participant, however, financial compensation will not be available.

The research participant will not be paid for taking part in this study.

#### **14.7 Informed Consent Processes**

The Principal Investigator or IRB approved named designate will explain the nature, duration, purpose of the study, potential risks, alternatives and potential benefits, and all other information contained in the informed consent document. In addition, they will review the experimental subject's bill of rights and the HIPAA research authorization form. Research subjects will be informed that they may withdraw from the study at any time and for any reason without prejudice, including as applicable, their current or future care or employment at City of Hope or any relationship they have with City of Hope. Research subjects will be afforded sufficient time to consider whether or not to participate in the research.

Should sufficient doubt be raised regarding the adequacy of comprehension, further clarifications will be provided. Prospective research subjects who cannot adequately comprehend the fundamental aspects of the research study with a reasonable amount of discussion, education and proctoring will be ineligible for enrollment. For those subjects who do comprehend the fundamental aspects of the study, consent will be obtained and documented, followed by eligibility testing. The research team will review the results of eligibility testing and determine if the subject is a candidate for study enrollment. No subjects will be enrolled into the study without first demonstrating full comprehension of the study and their rights as research subjects.

